### 9.2.3.13 Incidence of transaminitis

Incidence of transaminitis will be summarized and compared using Logit model, adjusting for stratification factors.

9.2.3.14 Incidence of subjects requiring Renal Replacement Therapy (RRT) after randomization

Incidence of subjects requiring Renal Replacement Therapy (RRT) after randomization will be summarized and compared using Logit model, adjusting for stratification factors.

9.2.3.15 Incidence of new bacterial, invasive fungal, or opportunistic infection

Incidence of new bacterial, invasive fungal, or opportunistic infection will be summarized and compared using Logit model, adjusting for stratification factors.

9.2.3.16 Change in size of lesion area by chest radiograph or CT

Change in size of lesion area by chest radiograph or CT will be summarized descriptively and compared using Logit model, adjusting for stratification factors.

9.2.3.17 Change from baseline in serum cytokine and chemokine levels at Days 3, 7, and 14

Change from baseline in serum cytokine and chemokine levels at Days 3, 7, and 14 will be summarized descriptively and compared using ANCOVA adjusting for stratification factors.

If the Normality assumption is not met, a non-parametric method or a rank –ANCOVA analysis i.e., an ANCOVA analysis on rank-transformed data will be used.

9.2.3.18 Change from baseline in CCR5 receptor occupancy levels for Tregs and macrophages at Days 3, 7, and 14

Change from baseline in CCR5 receptor occupancy levels for Tregs and macrophages at Days 3, 7, and 14 will be summarized descriptively and compared using ANCOVA adjusting for stratification factors.

If the Normality assumption is not met, a non-parametric method or a rank –ANCOVA analysis i.e., an ANCOVA analysis on rank-transformed data will be used.

9.2.3.19 Change from baseline in CD3+, CD4+ and CD8+ T cell count at Days 3, 7, and 14 Change from baseline in CD3+, CD4+ and CD8+ T cell count at Days 3, 7, and 14 will be summarized descriptively and compared using ANCOVA adjusting for stratification factors. If the Normality assumption is not met, a non-parametric method or a rank –ANCOVA analysis i.e., an ANCOVA analysis on rank-transformed data will be used.

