7.19. CHEST RADIOGRAPH OR COMPUTED TOMOGRAPHY SCAN

If clinically indicated by the treating physician, a chest radiograph or CT scan will be performed at Screening Visit (V1) and V5 (EOT)

7.20. REQUIREMENT OF MECHANICAL VENTILATION, NON-INVASIVE VENTILATION, SUPPLEMENTAL OXYGEN, VASOPRESSORS USE, RENAL REPLACEMENT THERAPY, ICU ADMISSION, AND HOSPITAL STAY

The incidence and duration, in days, of mechanical ventilation, non-invasive ventilation, supplemental oxygen, vasopressors use, renal replacement therapy, ICU admission and hospital stay will be assessed at Screening (V1) and V3, V4, and V5 (EOT).

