8.10.4. Efficacy Analyses

Primary Analysis

The ITT population will be the primary population for the analysis of the efficacy endpoints of the study.

Primary Endpoint

CONFIDENTIAL Page 82 of 108

The primary endpoint for this study is the proportion of subjects with Mortality at Day 28 between leronlimab and placebo. The difference in the Day 28 mortality between the leronlimab and placebo treatment groups will be compared using Logistic regression model.

Secondary Endpoints

To maintain the trial-wise Type I error rate at 0.05, a closed test procedure will be used for the secondary endpoints. The order of the secondary endpoints will prospectively specified in the SAP.

Analysis of the secondary and exploratory endpoints will be summarized according to the variable type:

- Continuous data summaries will include:
 - o If the Normality assumption is met, Analysis of Covariance (ANCOVA) would be used.
 - If the Normality assumption is not met, a non-parametric method or a rank ANCOVA analysis i.e., an ANCOVA analysis on rank-transformed data will be used.
- Categorical data summaries will be based on Logit model will be used.
- Time-dependent data: Cox proportional hazards model will be used to analyze time dependent data and to depict the time to event data.

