 Incidence of transaminitis, defined as an increase in alanine aminotransferase (ALT) and/or aspartate aminotransferase (AST) to > 5 times the upper limit of normal.

- Incidence of subjects requiring Renal Replacement Therapy (RRT) after randomization
- Incidence of new bacterial, invasive fungal, or opportunistic infection
- Change in size of lesion area by chest radiograph or CT
- Change from baseline in serum cytokine and chemokine levels at Days 3, 7, and 14
- Change from baseline in CCR5 receptor occupancy levels for Tregs and macrophages at Days 3, 7, and 14
- Change from baseline in CD3+, CD4+ and CD8+ T cell count at Days 3, 7, and 14

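### SAP 9.2.3.16 gives change in lesion area a Logit model, although the outcome reads as continuous and neither document defines a category or cut-off for it

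*SAP*

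**What the plan says.** SAP 3.3 lists the exploratory endpoint as "Change in size of lesion area by chest radiograph or CT"; protocol 8.2.3 lists the same endpoint. Neither entry adds a unit, grading scheme, responder definition or threshold. SAP 9.2.3.16 then sets the analysis: "Change in size of lesion area by chest radiograph or CT will be summarized descriptively and compared using Logit model", with adjustment for the stratification factors.

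Protocol 8.10.4 gives a general rule: "Analysis of the secondary and exploratory endpoints will be summarized according to the variable type". For continuous data, "If the Normality assumption is met, Analysis of Covariance (ANCOVA) would be used"; if normality fails, a non-parametric method or a rank "ANCOVA analysis i.e., an ANCOVA analysis on rank-transformed data will be used". For categorical data, "Categorical data summaries will be based on Logit model will be used".

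Protocol 7.19 and note 16 to the schedule of assessments (protocol Table 4-2) provide for a chest radiograph or CT at V1 and V5, and only where the treating physician finds it clinically indicated. No reading or scoring method is described.

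**The concern.** A binary Logit model needs a two-level outcome. Nothing in either document turns a change in area into one, so the model named in 9.2.3.16 does not match the endpoint it is meant to analyse. It also departs from the protocol's rule for continuous exploratory endpoints.

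What is at stake is prespecification. A programmer working from the SAP would have to choose the cut-off, and different cut-offs can give different answers. The SAP exists to settle such choices in advance.

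**Working it through.** The plan states no figure on this point, so the check is mainly a comparison of texts.

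**Step 1: does the protocol rule cover this endpoint?** Yes. Protocol 8.10.4 applies its variable-type rule to exploratory as well as secondary endpoints.

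**Step 2: how does SAP 9.2.3 treat its other endpoints?**

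| Type of endpoint | SAP sections | Method |
|---|---|---|
| Change in ordinal status, SOFA, SpO2, NEWS2, cytokines, receptor occupancy, T cells | 9.2.3.2, .3, .7, .11, .12, .17, .18, .19 | ANCOVA, rank-ANCOVA or non-parametric fallback |
| Proportions and incidences: extubation, ICU admission, start of ventilation, transaminitis, RRT, new infection | 9.2.3.4, .5, .6, .13, .14, .15 | Logit model |
| Change in lesion area | 9.2.3.16 | Logit model |

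Lesion area is the only change endpoint given a Logit model, and the only Logit endpoint in 9.2.3 that is not a proportion or an incidence. Its sentence opens like the ANCOVA endpoints (a descriptive summary, then a comparison) and closes with the clause used in the three incidence sections just before it. That pattern suggests a drafting slip, though the documents do not say so.

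**Step 3: could the Logit model mean an ordinal model?** Not by the SAP's own usage. SAP 9.2.2.2 calls its ordinal model a proportional odds model, and 9.2.3.2 analyses change on the 7-point scale by ANCOVA.

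**Step 4: what happens if the sentence is followed literally?** One data set was simulated to illustrate this. The inputs are assumptions, apart from the group sizes, which are the planned completers in protocol 8.3:

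- 246 subjects on leronlimab and 123 on placebo. Far fewer may be imaged in practice.
- Normally distributed change, true mean difference −5, SD 20, arbitrary units.
- Treatment as the only model term.

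A binary logit fit to the raw change stopped with an error, because the outcome must lie between 0 and 1. Linear models on the raw values and on the ranks both fitted. After dichotomising, the logit model fitted, and its result moved with the cut-off:

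| Response defined as change below | Log odds ratio | p |
|---|---|---|
| 0 | 0.46 | 0.041 |
| −10 | 0.44 | 0.059 |
| −20 | 0.61 | 0.044 |

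The same data fall on either side of 0.05 depending on a threshold the SAP does not give. This shows that the cut-off is a free choice. It does not estimate the effect in this trial.

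**The case against.** The strongest reply is that the documents never state the measurement scale. Radiograph and CT are interchangeable in the endpoint, and no reader or unit is named. Lesion change might have been meant as a graded reading, such as improved or not improved. A Logit model would then comply with protocol 8.10.4. This stands in part: continuous is the plain reading of a change in the size of an area, but it is an inference. It does not rescue the sentence, because a categorical outcome would need categories and none are given.

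A second reply is that SAP 2.6 keeps treatment blinded until database lock and protocol 8.10 requires the SAP to be approved before lock. That limits the room for a cut-off chosen in knowledge of treatment. It does not supply the cut-off.

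A reader might also infer stronger points that the documents do not support:

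- **That a logit model can never be fitted here.** It can, once the outcome is dichotomised, and a cumulative logit would fit ordered categories. The defect concerns the outcome as now defined.
- **That subjects never imaged would have lesion change imputed.** SAP 8.3 limits imputation to subjects with some baseline and post-baseline data. Read per variable, a never-imaged subject is not imputed; read per subject, that subject could be. The text does not settle which.
- **That a known share of information is lost.** The familiar 2/π, about 64% retained, assumes a normal outcome split at its median. The SAP specifies neither.

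**Conclusion.** The point holds. SAP 9.2.3.16 names a model that does not fit the endpoint on its plain reading, that conflicts with protocol 8.10.4, and that breaks the SAP's own pattern for change endpoints. As the outcome is defined, the analysis needs an unplanned choice of cut-off.

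This rests on one assumption, that lesion change would be recorded as a measured quantity. If it was to be recorded in categories, the conflict with the protocol falls away and the missing category definitions remain.

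The impact is small. The endpoint is exploratory, lies outside the fixed-sequence testing of secondary endpoints in SAP 8.4, and affects neither the primary mortality test nor the type I error. No numerical loss can be attached to it from the documents.

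**What to change.** In SAP 9.2.3.16, replace the Logit model with ANCOVA adjusting for the stratification factors, and for baseline lesion area where it was measured. Add the rank-ANCOVA or non-parametric fallback already used in the sibling sections. If a categorical outcome was intended, keep the Logit model but state the categories, the cut-off and how images are read, before unblinding.

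In either case, add a sentence saying that the result describes subjects imaged because it was clinically indicated.

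Limiting the analysis to subjects with images of the same modality at both V1 and V5, without imputation, is not part of this fix. It would condition on survival to V5 and on a decision to image made after randomisation, and it would depart from the planned multiple imputation.

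The cost is two or three sentences in the SAP for the ANCOVA route, and somewhat more if categories and a reading method must be written. Neither route changes the sample size or the primary analysis, and the ANCOVA route calls for no new assessments.

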## 9.3 Analysis of Safety Data

The Safety population will be used for the analysis of safety assessments.

#### 9.3.1 Adverse Events

Adverse events will be coded using the most recent version of Medical Dictionary for Regulatory Activities (MedDRA). Treatment Emergent AE's (TEAE) are defined as events with an onset on or after the first treatment. TEAEs will be summarized by System Organ Class and preferred term by treatment group. The following TEAE summaries will be provided:

- Overall (i.e., regardless of severity or relationship to treatment);
- By intensity (mild, moderate, severe, life threatening or death);
- By causality (definitely, probably, possibly, remotely or unrelated);
- By impact on study treatment (dose increased, dose not changed, dose rate reduced, dose reduced, drug interrupted, drug withdrawn, not applicable, or unknown).

In addition, separate summaries of serious adverse events, and adverse events resulting in discontinuation of study treatment will be presented.

## 9.3.2 Clinical Laboratory Evaluations

All available results of the clinical laboratory evaluations will be listed and summarized. Laboratory evaluations include serum biochemical, hematologic, coagulation, urinalysis, and serum/urine

pregnancy (if applicable).

### 9.3.2.1 Laboratory Values over Time

Summary statistics of raw data and change from baseline values for each laboratory parameter will be presented. Data will be summarized as appropriate to the variable type.

For change from baseline summaries, subjects with an undefined change from baseline, because of missing data, will be excluded.

### 9.3.2.2 Individual Subject Changes (Shift Tables)

Individual subject changes will be identified through shift tables. Shift tables will be presented for each laboratory parameter with counts and percentages of subjects, for shift (change) from baseline.

# 9.3.2.3 Clinically Significant Abnormalities

A by-subject listing of treatment-emergent clinically significant laboratory values, by treatment group, will be prepared.

## 9.3.3 Vital Signs

Tabulations of raw data and change from baseline values will be presented by time point for each vital sign parameter including temperature, pulse, respiratory rate, systolic and diastolic blood pressure.

Tabulations will include the number of observations, mean, standard deviation, median, and minimum and maximum values. For change from baseline summaries, subjects with an undefined change from baseline, because of missing data, will be excluded.

#### 9.3.4 Electrocardiogram (ECGs)

The ECG parameters include ventricular rate (beats per minute), PR interval (msec), QRS interval (msec), QT interval (msec), and QTc interval (msec).

#### 9.3.4.1 ECG Values over Time

Descriptive statistics of raw data and change from baseline values for each ECG measurement will be presented by treatment group. For change from baseline summaries, subjects with an undefined change from baseline, because of missing baseline data, will be excluded.

### 9.3.4.2 Individual Subject Changes (Shift Tables)

Individual subject changes will be identified through shift tables. Shift tables will be presented for the investigator ECG interpretation (i.e., Normal, Abnormal (not clinically significant) and Abnormal (clinically significant)) with counts and percentages of subjects, by treatment group, for shift (change) from baseline, using the normal ranges.

#### 9.3.5 Physical Examination

All physical examination findings will be listed and/or summarized by treatment group.

#### 9.4 Analysis of Open-Label Arm Data

The data from the single arm, non-randomized, open-label phase will be captured in the same EDC system. The data from this phase of the study will mainly be used for safety analysis as part of the safety population using the metrics laid out in Section 9.3 of this SAP. In addition, the data from this phase will also be used as a supportive efficacy analysis by pooling the data from this phase with the Leronlimab group of the randomized phase. The endpoints to be assessed include:

- All-cause mortality
- Proportion of patients achieving a category of 6 or higher at Days 14 and 28 (on a 7-point ordinal scale).

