8.10.5. Supportive Analysis

To assess the consistency of the Primary Analysis results, supportive analysis will be conducted using the Intent to Treat (ITT) and Per Protocol (PP) populations. Statistical methodology for the supportive analyses will be the same as that of the primary analysis, with the exception of the analysis population used.

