### 2.3 Study Treatments

There will be two treatment groups in the study as detailed in Table 2-2 below:

**Table 2-2:** Treatment Groups

Study Drug	Dosage IP Form concentration Dosing Frequency and Amount		Route of Administration		
Leronlimab (PRO 140 700 mg)	Parenteral	175 mg/mL	2 injections of leronlimab (PRO 140 2 X 2 mL/inj.) per week on opposite sides of abdomen	SC injection	
Placebo	Parenteral solution	0 mg/mL	2 injections of placebo (2 X 2 mL/inj.) per week on opposite sides of abdomen	SC injection	

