## 7.4 Safety Population

The **Safety Population** will include all subjects who have received one dose of Study Treatment. This population will be used for the analysis of safety parameters or measurements. This population will include the subjects from the single arm, non-randomized, open-label phase that received leronlimab.

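### Non-randomized open-label subjects are pooled into the leronlimab group for efficacy and, on a literal reading, into the leronlimab column of the final safety tables

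*SAP*

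**What the plan says.** **Efficacy.** SAP 9.4 provides for a "supportive efficacy analysis by pooling the data from this phase with the Leronlimab group of the randomized phase". The endpoints are all-cause mortality, with no day given, and the proportion in category 6 or higher at Days 14 and 28. No model, adjustment or comparator is stated.

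**Meaning of supportive.** Under Protocol 8.10.5, which sets out how the consistency of the primary result is assessed, "supportive analysis will be conducted using the Intent to Treat (ITT) and Per Protocol (PP) populations". It adds: "Statistical methodology for the supportive analyses will be the same as that of the primary analysis, with the exception of the analysis population used". Both of those populations contain randomized subjects only.

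**Safety.** SAP 7.4 says of the Safety Population: "This population will include the subjects from the single arm, non-randomized, open-label phase that received leronlimab". SAP 9.3 then states: "The Safety population will be used for the analysis of safety assessments". The layout for adverse events in SAP 9.3.1 is: "TEAEs will be summarized by System Organ Class and preferred term by treatment group". SAP 9.3.4 lays out the ECG summaries by treatment group, and SAP 9.3.5 says: "All physical examination findings will be listed and/or summarized by treatment group". On the groups themselves, SAP 2.3 says: "There will be two treatment groups in the study". These are leronlimab and placebo. No open-label column and no randomized-only version of the final safety tables is specified.

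**The open-label phase.** SAP 2.2 places it after randomized enrolment is complete. Protocol 8.3 gives its purpose as access to the drug. Everyone in it receives leronlimab (Protocol 4.2.1).

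**The concern.** A pooled leronlimab figure is no longer protected by randomization. The open-label subjects come later in calendar time, and their case mix may differ. Background care may differ as well, because SAP 8.5 records that off-label COVID-19 co-treatment was allowed without restriction. For adverse events, and possibly for the discharge decision behind category 6 or higher, knowing the treatment is a further route to bias. For mortality, only case mix and background care apply. Whatever the source, the difference enters the leronlimab side alone, since placebo has no open-label counterpart.

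The label adds to the problem. The protocol uses *supportive* for analyses that check the primary result in randomized subjects with the primary method. SAP 9.4 applies the same word to a partly non-randomized group and does not say whether that meaning carries over. It could be read as a descriptive rate or as a repeat of the primary comparison against placebo. For mortality, that choice should not be left open until after unblinding.

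**Working it through.** **Inputs.** SAP 4 gives 260 leronlimab and 130 placebo subjects randomized, 246 and 123 completers, 5% dropout, about 100 open-label subjects, and planned Day 28 mortality of 45% on placebo against 30% on leronlimab.

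**Check of the plan's own sample size.** With unpooled variance and 2:1 allocation, placebo n = (1.960 + 0.842)² × (0.45×0.55 + 0.30×0.70/2) / 0.15² = 122.97. This rounds up to 123, for a total of 369, as stated. Inflation for dropout gives 369/0.95 = 388.4, so 389; the stated 390 keeps 2:1 at 260 and 130.

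**Non-randomized share** = open-label n / (randomized leronlimab n + open-label n).

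| Open-label n | Randomized leronlimab n | Share |
|---|---|---|
| 100 (SAP 4) | 260 | 100/360 = 27.8% |
| 100 (SAP 4) | 246 completers | 100/346 = 28.9% |
| 50 (assumed) | 260 | 50/310 = 16.1% |
| 200 (assumed) | 260 | 200/460 = 43.5% |

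The range is shown because the documents disagree on the size of this phase. SAP 4 and Protocol 8.3 say about 100 and leave enrolment open until the sponsor and/or FDA close it. Protocol 3 caps it at 100. Under that cap, 27.8% is the maximum with 260 randomized.

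**Movement of the leronlimab figure** = share × (open-label rate − randomized leronlimab rate). At 27.8%, a 1-point movement needs a difference of 1/0.278 = 3.6 points. The documents give no between-phase difference, so 5, 10 and 15 points are assumed:

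- 5 points: 0.278 × 5 = 1.4 points
- 10 points: 0.278 × 10 = 2.8 points
- 15 points: 0.278 × 15 = 4.2 points

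The direction can be either way. The same arithmetic applies to mortality, category 6 or higher and adverse event incidence.

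**Hypothetical test against placebo.** SAP 9.4 states no such test; this shows only what would follow if one were run. Assume no drug effect, 45% mortality in both randomized arms, and open-label mortality lower by the shift s. Then:

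- pooled rate p = (260×0.45 + 100×(0.45 − s))/360
- d = 0.45 − p
- SE = √(0.45×0.55/130 + p(1 − p)/360)
- rejection rate = Φ(d/SE − 1.96) + Φ(−d/SE − 1.96)

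| s | p | d | SE | Two-sided rejection rate |
|---|---|---|---|---|
| 0 | 0.4500 | 0 | 0.0509 | 5.0% |
| 0.05 | 0.4361 | 0.0139 | 0.0509 | 5.9% |
| 0.10 | 0.4222 | 0.0278 | 0.0508 | 8.5% |
| 0.15 | 0.4083 | 0.0417 | 0.0507 | 13.0% |

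A pooled-variance test gives 5.9%, 8.6% and 13.2% for the three shifts.

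**The case against.** Five points can be made for the plan.

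- **Column assignment is inferred.** SAP 9.4 uses pooling language only for efficacy. For safety it says the open-label data form part of the Safety Population, and no sentence puts them in the same column as randomized leronlimab subjects. SAP 9.3.2.1 (laboratory) and 9.3.3 (vital signs) do not mention treatment group, and SAP 10 gives only table headings. This stands as a caveat on the safety half. Still, with two groups defined and summaries by group, the leronlimab column is where the written rules put these subjects.
- **No placebo test is stated.** Correct. The rejection rates above describe an analysis the SAP does not specify and carry no weight in the conclusion.
- **Protocol 8.10.5 names only ITT and PP.** Its same-method rule therefore need not reach SAP 9.4. That is a fair reading, but the SAP does not say so.
- **The phases are alike on paper.** The study flow is the same, no separate eligibility criteria are given, and no passage documents a difference in patients or care. This makes a large difference less certain, but it does not replace randomization or concurrent control.
- **Consequences are limited.** The primary and secondary analyses use mITT, ITT and PP. The interim safety summaries use randomized treated subjects (SAP 5.1.3). Protocol synopsis, Safety Assessments, plans no inferential statistics. All of this stands and bounds the point; it does not remove it, because descriptive leronlimab and placebo columns are still read against each other.

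**Conclusion.** The concern holds and should be fixed. The efficacy pooling is explicit. Entry into the leronlimab safety column is the literal consequence of SAP 7.4, 9.3 and 2.3 taken together, though it is not stated in so many words.

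At planned sizes, 27.8% of the pooled leronlimab group would be non-randomized, and the same fraction of any between-phase difference would pass into that group's figures. The share rests on 260 randomized leronlimab subjects and about 100 open-label subjects. The size and direction of any actual difference are unknown.

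The pooling cannot change the primary test or the secondary testing sequence. What it weakens is the pooled efficacy presentation and the final leronlimab-versus-placebo safety displays.

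**What to change.** **SAP 9.4.** Report open-label mortality, with the day named, and category 6 or higher at Days 14 and 28 descriptively in a separate column. If a pooled leronlimab figure is kept, label it as non-randomized and not compared with placebo, and state that it is not a supportive analysis in the sense of Protocol 8.10.5.

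**SAP 7.4 and 9.3.** Limit the leronlimab-versus-placebo safety tables to randomized treated subjects, the set SAP 5.1.3 already uses for the interim safety summaries. Give open-label subjects their own column. A column for all leronlimab-exposed subjects may be added, without comparison to placebo.

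**Cost.** SAP and table-shell wording plus one extra column. The leronlimab denominator in the placebo safety comparisons falls from about 360 to about 260 at planned sizes. The full exposure count is kept if the all-exposed column is added. No new data are needed.
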